2.6 Intervention

Sacrospinous hysteropexy will be performed in a traditional and standardized manner in accordance with our surgical policy. Any other concomitant procedures (e.g.,

anterior and/or posterior colporrhaphy, cystoscopy, etc.) will be performed in accordance with each surgeon's preferred technique.

Operative management: All patients will be operated by the vaginal route. They are prepared under strict aseptic conditions in the dorsal lithotomy position. The bladder is emptied preoperatively with a thin disposable catheter and antibiotic prophylaxis (cefazolin) is administered before incision. A vasoconstricting solution (combination of vasopression and NaCl) is administered and a high posterior colpotomy is made towards the posterior cervix. Blunt preparation towards the right Spina ischiadica to visualize the right sacrospinous ligament. Once 4 cm of ligamentum sacrospinale are visualised, two sutures will be placed through the ligament approximately 2 cm medial of the spina ischiadica. Depending on preoperative randomization, patients will receive either PDS sutures (PDS 0) or prolene (2-0) sutures. This suture will then be placed through the posterior cervical wall, but not yet knotted. First, the colpotomy will be closed via absorbable sutures (2/0 vicryl). Should additional procedures such as anterior and/or posterior colporrhaphy be indicated, they will be performed at this stage. Only after, the pre-laid fixation sutures will be tied, whereby the portio will come to lie about 4-6 cm cranial of the level off the vulva towards the sacrospinous ligament. Participating surgeons will be defined as high volume surgeons in prolapse surgery and will also be part of the urogynaecologic core team.

Perioperative management: is also standardized and includes preoperative single-shot antibiotics as well as vaginal pack and an indwelling urinary catheter for 24 hours after the surgical procedure. Patients will have postvoid residual volume measurement at the first postoperative day (when urinary catheter is removed). A postvoid residual volume of $2 \times < 150$ ml is defined as normal and no further follow-ups are necessary. Postvoid residual volumes of > 150 mL or greater will be

considered as abnormal. These patients' volumes will continue mechanical bladder drainage via clean intermittent (self)-catheterisation until the postvoid residual volumes are consistently less than 150 ml. Patients will receive standard analgesic therapy in accordance with the local hospital protocol (Metamizol 1g intravenously, 3 times a day).

Postoperative Management: The patients are instructed to rest for 2 weeks after the operation (not to work, to do sport, to do the cleaning and to carry more than five kilos). They are allowed to return to work after 4 weeks and to take part in sport or have intercourse after 6 weeks. Follow-up visits are scheduled postoperative after 4-6 weeks, 6 months and 1 year in our outpatient clinic due to our study protocol.

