2.1 Study hypothesis

Primary study hypothesis is that patients receiving a sacrospinous hysteropexy with non-resorbable Prolene sutures (study group) experience a better subjective symptom improvement (evaluated by the prolapse domain score of the Deutscher Beckenboden Fragebogen [11]) assessed at 12 months after surgery, than patients with resorbable PDS sutures (control group).

The secondary hypotheses are, that the study group will have:

- better anatomical outcomes (better rate anatomical outcome in each compartment (change in POP-Q values from baseline) [12]),
- better condition-specific quality of life scores (changes in questionnaire from baseline),
- less postoperative complications (haematoma, vesico-vaginal fistula, ureteral obstruction, urinary tract infection, incomplete bladder emptying, overactive

bladder or stress incontinence symptoms, suture erosion, vaginal wound dehiscence, infection or granulation tissue, etc),

- lower use of pain killers for buttock pain during the hospital stay and in the 12 months postoperative period
- lower pain levels (assessed through the standardised Visual Analog Scale (VAS) and Numeric Rating Scale (NRS) [13]) at postoperative day 1, at discharge, at 4 to 6 weeks, 6 and 12 months.

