2.2 Study design

This trial is a single-centre, prospective, randomized trial conducted with the aim of determining the superiority of non-absorbable prolene over absorbable PDS suture material with regard to the primary outcome in POP patients undergoing sacrospinous hysteropexy. The study will be a single-blind study, as it is impossible to blind the study surgeon for the surgical procedure to which the subject is assigned. However, all outcome assessors and the subjects will be blinded to the assigned treatment. Postoperative follow-up will take place after 4-6 weeks, 6 months and 12 months. Patients will undergo a standardized urogynaecologic examination that includes assessment of prolapse with POP-Q measurement [12]. Furthermore subjective outcome will be assessed with standardized questionnaires – our study participants will receive the German version of the pelvic floor questionnaire [11].

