2.7 Inclusion and exclusion criteria

Inclusion criteria

- Anterior vaginal wall prolapse beyond the hymen (POP-Q point Aa or Ba >0) with a central defect.
- Apical vaginal vault prolapse beyond the hymen (POP-Q point C >0) with a central defect. Vaginal bulge symptoms
- Uterus-preserving reconstructive surgery via vaginal sacrospinous hysteropexy is planned

Exclusion criteria

- History of hysterectomy

- Reconstructive pelvic floor surgery using mesh or obliterative surgery is planned
- Reconstructive pelvic floor surgery with hysterectomy is planned
- Prior reconstructive pelvic floor surgery with mesh
- Known pelvic malignancy
- Known inflammatory disease
- Current systemic glucocorticoid or immunosuppressant treatment.
- Subject is unable or unwilling to participate

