2.10 Data analysis

Statistical analysis will be performed using SPSS and Excel software. Data will be calculated and graphed as mean plus minus standard error of mean (SEM).

Metric variables will be reported by mean and standard deviation resp. median and IQR, categorical variables will be reported by frequencies per group and timepoint. The primary outcome subjective symptom improvement after 12 months in either group will be analyzed by a t-test or a Man-Whitney-U-test depending on the distribution of improvements.

For the secondary endpoints, differences of rates of adverse events between the two treatment groups will be analysed by a Chi-squared test. Blood loss, use of pain killers and changes in condition-specific quality of life will be compared between groups analogously to the primary outcome.

Changes in POP-Q values from baseline over time will be analysed by a linear mixed model with fixed effects group, time, POP-Q point, age and BMI and random effect intercept per patient. Statistical significance will be set 0.05. No correction for multiple testing is performed because only one main hypothesis is considered.

3. Research facility

The patient screening will be performed at the urogynaecologic outpatient clinic of the Department of General Gynaecology and Gynaecologic Oncology, Medical University of Vienna, Austria. Infrastructure needed for this study is already present.

4. Ethical and legal aspects

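### Women are randomised before surgery although the arms do not differ until the ligament is exposed; generating the allocation in theatre would avoid losses after randomisation and keep the surgeon unaware of the arm when deciding whether to proceed

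*Combined protocol and SAP*

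**What the plan says.** All references are to the combined protocol and SAP.

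- **Timing of randomisation, section 2.6:** "Depending on preoperative randomization, patients will receive either PDS sutures (PDS 0) or prolene (2-0) sutures". The exact moment before surgery is not given.
- **When the allocation is first used, section 2.6:** "Once 4 cm of ligamentum sacrospinale are visualised, two sutures will be placed through the ligament". Up to that step the operation is the same in both arms.
- **Eligibility, section 2.7:** "Uterus-preserving reconstructive surgery via vaginal sacrospinous hysteropexy is planned". The operation has to be planned; it need not have been found feasible.
- **Concomitant repairs, section 2.6:** "Should additional procedures such as anterior and/or posterior colporrhaphy be indicated, they will be performed at this stage". This stage comes after the fixation sutures have been laid and before they are tied.
- **Blinding, section 2.2:** the surgeon cannot be blinded, while "all outcome assessors and the subjects will be blinded to the assigned treatment".
- **Wording of the groups, section 2.1:** the study group is "patients receiving a sacrospinous hysteropexy with non-resorbable Prolene sutures (study group"); its members are expected to do better "than patients with resorbable PDS sutures (control group").
- **Primary analysis, section 2.10:** "The primary outcome subjective symptom improvement after 12 months in either group will be analyzed by a t-test" or a Mann-Whitney U test. The section names no intention-to-treat, per-protocol or as-treated set.
- **Allowance for loss, section 2.9:** 20% dropout, which takes 21 per group to 26.

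**The concern.** Between randomisation and the first step at which the arms differ, a woman's operation can be cancelled, exposure of the ligament can fail, or the procedure can be converted to another one. She then counts as randomised, has used a place in a block of four, and has received neither suture. In this trial randomising so early has no evident benefit, because nothing done before the ligament is exposed depends on the allocation.

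Two things are at stake. First, a surgeon who already knows the arm may be influenced by it when deciding whether to go on with the hysteropexy. A loss that depends on the arm is not protected by randomisation. Second, such women cost power whichever way they are handled. Dropping them reduces the numbers, and keeping them as randomised dilutes the contrast between sutures. With 26 women per arm, a few cases are noticeable. The plan does not say which handling applies.

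**Working it through.** **Inputs.** From section 2.9: SD of the score 2.2 before and after surgery, correlation 0.5, difference in change 2, power 80%, 21 evaluable per group, 20% dropout, 26 enrolled per group. From section 2.10: significance level 0.05. Sidedness is not stated. Two-sided is assumed because it reproduces the plan's number.

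**Step 1: reproduce the plan's figure.**
- SD of change = √(2.2² + 2.2² − 2 × 0.5 × 2.2 × 2.2) = 2.2.
- Standardised difference = 2 / 2.2 = 0.909.
- A two-sided two-sample t-test at 0.05 with 80% power needs 20.0016 per group, rounded up to 21. A one-sided test would need only 16.
- Power with 21 per group is 82.0%.
- 21 / 0.8 = 26.25, which rounds up to 27. The plan enrols 26, and 26 × 0.8 = 20.8. This one-woman gap does not affect the present point.

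**Step 2: assumed counts.** The documents give no rate of cancellation, failed exposure or conversion. The counts k = 1, 2, 3 per arm are assumptions, about 5%, 10% and 14% of 21.

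*Dropped* means that n per arm is 21 − k and the difference stays 2. *Kept* means that n stays 21 and these women contribute no suture contrast, so the difference is 2 × (1 − k/21). Power is from the noncentral t distribution with SD 2.2.

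| k per arm | Dropped: n per arm | Dropped: power | Kept: difference | Kept: power |
|---|---|---|---|---|
| 0 | 21 | 82.0% | 2.00 | 82.0% |
| 1 | 20 | 80.0% | 1.90 | 78.2% |
| 2 | 19 | 77.8% | 1.81 | 73.9% |
| 3 | 18 | 75.5% | 1.71 | 69.3% |

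**Step 3: sensitivity to the dropout allowance.** The dropped columns treat these losses as additional to the 20% already allowed. If 2 of 26 are removed first and 20% of the remainder then drop out, (26 − 2) × 0.8 = 19.2 per arm remain and power is 78.3%. If the 2 of 26 are kept and 20% of all 26 drop out, the difference is 2 × (1 − 2/26) = 1.85, n is 20.8 and power is 75.2%. If the dropped women are simply part of the 20%, there is no further loss of power.

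**Step 4: the passages side by side.** Section 2.1 words the groups by the suture received. Section 2.6 makes the suture follow from the randomisation. Section 2.2 speaks of assigned treatment, but only in connection with blinding. Section 2.10 refers to the groups without saying how membership is determined. None of these is a rule for a woman who gets neither suture, or the other one.

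**The case against.** A reader might infer from section 2.1 that a woman given the other suture changes arm and that a woman given neither belongs to no group. The documents do not support that. Section 2.1 states a hypothesis, not an analysis rule; no section moves or excludes anyone; and section 2.10 is compatible with analysis as randomised. What can be said is that the rule is missing.

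A reader might also infer that preoperative randomisation is an error. It is not. If every woman is analysed as randomised, the comparison remains valid, and later allocation only reduces the number of women who dilute it. This stands, and it makes the timing a matter of better design. The as-randomised rule does not, however, recover the power lost in the kept column, and it does not keep the arm from the surgeon at the decision to proceed.

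The event rate is assumed, and section 2.6 restricts surgery to high-volume surgeons, so such events may be rare. The loss from dropping women may lie partly or wholly within the 20% allowance. Both points stand and limit the size of the problem. It is also conjecture that easier anatomy would collect in one arm: the documents give no reason why conversion should differ by suture, and this bias has not been quantified.

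Finally, delaying the allocation does not blind the surgeon for the concomitant repairs, since these follow the laying of the sutures under either timing. That stands too.

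**Conclusion.** The point holds as a recommended design improvement together with a missing rule. The plan randomises earlier than it needs to, allows avoidable losses after randomisation, lets an unblinded surgeon know the arm when deciding whether to proceed, and leaves the analysis of women without their allocated suture open. It does not prescribe an as-treated analysis.

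With one to three affected women per arm, power would fall from 82% to between 80% and 75% if they are dropped beyond the dropout allowance, or to between 78% and 69% if they are kept without a suture contrast. These figures rest on the plan's own SD and difference, on a two-sided test at 0.05, and on counts that are assumptions. With no such events nothing is lost, and the stated 21 per group stands.

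**What to change.** 1. **Section 2.6:** have the existing randomizer generate the allocation in theatre, only after the ligament is exposed and hysteropexy is confirmed as feasible. The allocation should be generated then, not merely opened: if it already existed, the woman would already have been randomised and would have used a place in a block. Women who do not reach this point are logged as consented but not randomised. The parity stratum can be entered beforehand.
2. **Section 2.6:** have the surgeon record the planned concomitant repairs before the allocation is generated. This documents later departures from the plan; it does not blind the surgeon.
3. **Sections 2.1 and 2.10:** define the groups by assigned suture and analyse every randomised woman in her assigned group, whatever was done afterwards. Record the suture actually used, and present any as-treated analysis as supplementary. Missing 12-month scores need their own rule.

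**Cost.** A change of wording, a short intraoperative step, both sutures at hand, and some consented women who are never randomised. The documents do not say how the randomizer is accessed, so who would operate it from theatre has to be settled. If allocation in theatre proves impracticable, item 3 should still be adopted, since it secures the validity of the comparison, though not the power.

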2.7 Inclusion and exclusion criteria

Inclusion criteria

- Anterior vaginal wall prolapse beyond the hymen (POP-Q point Aa or Ba >0) with a central defect.
- Apical vaginal vault prolapse beyond the hymen (POP-Q point C >0) with a central defect. Vaginal bulge symptoms
- Uterus-preserving reconstructive surgery via vaginal sacrospinous hysteropexy is planned

Exclusion criteria

- History of hysterectomy

- Reconstructive pelvic floor surgery using mesh or obliterative surgery is planned
- Reconstructive pelvic floor surgery with hysterectomy is planned
- Prior reconstructive pelvic floor surgery with mesh
- Known pelvic malignancy
- Known inflammatory disease
- Current systemic glucocorticoid or immunosuppressant treatment.
- Subject is unable or unwilling to participate

2.8 Data collection

At baseline, the following data will be collected: demographics and medical history data (age, body mass index, parity, menopausal and hormone therapy status, nutritional status, current smoking, previous hysterectomy and previous anti-incontinence surgery), and medical comorbidities (diabetes mellitus, connective tissue disorders), and data from the standardized urogynaecologic examination (POP-Q examination during maximal Valsalva, genital hiatus measurements and ultrasound of cervix, uterus, bladder, pelvic floor muscles and levator ani muscle hiatus).

Urogynaecologic examination evaluations is made using the POP-Q measurement system on maximum Valsalva effort in the seated semi-lithotomy position (a 45° upright sitting position). Objective anatomical cure is defined as a Ba point < -1. Symptoms, quality of life and sexuality are evaluated with the Deutscher

Beckenboden-Fragebogen. This Pelvic Floor Questionnaire consists of four domains: bladder, bowel, pelvic organ prolapse and sexual function. In every domain various questions assess severity and condition-specific quality of life. Every question is scored on a scale from zero to four. The sum of each individual domain is divided by the maximum reachable score and multiplied by ten, giving a value between zero (0=no symptoms) and ten (10=maximum of symptoms) for each of the domains. Baessler et al. has published the results of the validation study and scoring system [11].

To evaluate nutrition status, patients will receive the "Mini Nutritional Assessment"-Fragebogen (<https://www.dgem.de/sites/default/files/PDFs/Screening/MNA-SF%20Deutsch-240513.pdf>) and laboratory testing of albumin, electrolytes (sodium, potassium, magnesium, phosphate, and calcium), haematocrit, creatinine, blood urea nitrogen, and bilirubin.

Patients will be asked to complete the standardised Visual Analog Scale (VAS), Numeric Rating Scale (NRS) [13] and answer the following questions:

- "Do you experience a sensation of bulging or protrusion from the vagina?" and "Do you have a bulge or something fallen out that you can see in the vagina?" [6]
- "Do you experience pain in the rump?" and "Do you experience pain in the lower back?" and "Do you experience pain while walking?" [6]
- "What rate of postoperative recurrence would you accept and still opt for the surgery?" [14].

Furthermore, patients will answer the "Patient Global Impression of Improvement (PGI-I)" as it takes little effort for the patient and allows a precise result in terms of the rate of improvement after the operation [15]. One of the following answers can be given by each patient:

1. A lot better.
2. Much better.
3. A little better.
4. no change.
5. A little worse.
6. Much worse.
7. A lot worse.

Scheduled in-person follow-ups will occur at 4 to 6 weeks, 6 and 12 months after the operation. Each check-up will include a full urogynaecologic clinical examination including POP-Q, ultrasound and bloodwork as well as a written questionnaire identical to the one at baseline. In addition, an update of current medications, an assessment of new or continuing pelvic floor disorders and adverse events that occurred since the previous evaluation will be obtained by the study coordinator at each visit. All data will be anonymized and collected using case report forms by examiners or trained research coordinators who are blinded to the treatment assignment.

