2.8 Primary and secondary outcome measures

The primary outcome is subjective symptom improvement (evaluated by the prolapse domain score of the Deutsche Beckenboden Fragebogen) assessed at 12 months after surgery.

The secondary outcomes are the anatomical outcomes (the rate of suboptimal anatomical outcome in each compartment (POP-Q point, change in POP-Q values from baseline), condition-specific quality of life (any changes in questionnaire Deutscher Beckenboden Fragebogen from baseline), postoperative complications (haematoma, vesico-vaginal fistula, ureteral obstruction, urinary tract infection, incomplete bladder emptying, overactive bladder or stress incontinence symptoms, suture erosion, vaginal wound dehiscence, infection or granulation tissue, etc), and use of pain killers during the hospital stay. In addition, patients' pain level will be assessed through the standardised Visual Analog Scale (VAS), Numeric Rating Scale (NRS) [13] and the earlier specified questions, patients' improvement rate will be assessed through the "Patient Global Impression of Improvement (PGI-I).

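### The only anatomical cure rule looks at point Ba and sets no condition on point C, the apex that the randomised suture suspends

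*Combined protocol and SAP*

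**What the plan says.** **Cure rule.** Section 2.8 Data collection states: "Objective anatomical cure is defined as a Ba point < -1". No other numeric threshold for anatomical success, failure or recurrence appears in the document.

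**What is randomised.** Section 2.6: "Depending on preoperative randomization, patients will receive either PDS sutures (PDS 0) or prolene (2-0) sutures". The suture is passed through the sacrospinous ligament, and then: "This suture will then be placed through the posterior cervical wall, but not yet knotted". Tying it draws the cervix cranially.

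**What is not randomised.** Section 2.6 on anterior and posterior repair: "Should additional procedures such as anterior and/or posterior colporrhaphy be indicated, they will be performed at this stage". Their technique is left to the surgeon: "anterior and/or posterior colporrhaphy, cystoscopy, etc.) will be performed in accordance with each surgeon's preferred technique".

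**Entry.** Section 2.7 lists an anterior criterion, "Anterior vaginal wall prolapse beyond the hymen (POP-Q point Aa or Ba >0) with a central defect", and an apical one, "Apical vaginal vault prolapse beyond the hymen (POP-Q point C >0) with a central defect".

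**Outcomes and analysis.** Section 2.1 hypothesises better anatomical outcomes compartment by compartment. Section 2.8 Primary and secondary outcome measures lists "the rate of suboptimal anatomical outcome in each compartment (POP-Q point, change in POP-Q values from baseline", with no threshold for a suboptimal result. Section 2.10 analyses POP-Q change in a linear mixed model with main effects for group, time, POP-Q point, age and BMI and a random intercept per patient.

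**The concern.** The compared suture acts directly on the apex, which POP-Q records as point C. The one cure rule in the plan reads only the anterior wall, which is also acted on by a repair that is not randomised. The plan promises an anatomical comparison in every compartment but supplies a cut-off for one of them. If Ba < -1 were reported as the trial's anatomical cure rate, it would not say whether the suture under study held the cervix. With the apical and posterior thresholds left open, they could also be chosen after the results are known.

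**Working it through.** **1. The plan's own figure.** The plan gives no sample size or power for anatomical cure. The primary-outcome calculation in section 2.9 supplies the group size used below.
- SD of change = sqrt(2.2² + 2.2² - 2 × 0.5 × 2.2 × 2.2) = 2.2.
- For a difference of 2, two-sided 0.05 (sidedness is not stated) and 80% power, the two-sample t-test solves at 20.0016, so 21 per group (power 0.82 at 21).
- Enrolling 26 with 20% dropout leaves 26 × 0.8 = 20.8, about 21.

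The figure reproduces and does not depend on the cure rule.

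**2. The rule applied to two possible results.**

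| 12-month result | Ba < -1? | Plan's label | State of the apex |
|---|---|---|---|
| Ba = -2, C = +1 | yes | cured | C > 0, so the apical entry criterion is still met |
| Ba = 0, C = -6 | no | not cured | suspension held |

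Both labels follow from the wording alone. The documents do not say how often either pattern would occur.

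**3. Does the mixed model recover the apex?** As listed, the expected change is: intercept + β1·group + time effect + point effect + age and BMI terms. The difference between arms is β1 at every point, whether Ba, C or Bp. If the true effect were d at C and zero at the other points, and k points entered in equal numbers, β1 would estimate about d/k. The POP-Q point term lets the mean change differ between points but not the group effect. Without a group-by-time term, the effect is also averaged over visits and is not specific to 12 months. The model gives no rate in any compartment.

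**4. How much apical difference could the Ba rule lose?** This needs assumptions. Let p be the proportion in whom the suspension holds, a the proportion with Ba < -1 among those held, and b the proportion with Ba < -1 among those failed, with a and b equal in both arms. Then the cure rate is p·a + (1 - p)·b, and the difference between arms is (p1 - p2)(a - b).

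Take p = 0.90 v 0.70 (assumed) and 21 per group. Power is the normal approximation, two-sided 0.05: Φ{[Δ√n - 1.96√(2p̄(1 - p̄))] / √(p1(1 - p1) + p2(1 - p2))}, where p1 and p2 are now the two cure rates, Δ their difference and p̄ their mean.

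| a | b | Ba cure rates | Difference | Power |
|---|---|---|---|---|
| 1 | 0 | 90% v 70% | 20 points | 0.36 |
| 0.8 | 0.2 | 74% v 62% | 0.20 × 0.6 = 12 points | 0.13 |
| 0.7 | 0.4 | 67% v 61% | 0.20 × 0.3 = 6 points | 0.06 |
| equal | equal | same | 0 | none beyond 0.05 |

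For the first row: [0.20 × √21 - 1.96 × √(2 × 0.8 × 0.2)] / √(0.09 + 0.21) = (0.917 - 1.109) / 0.548 = -0.35, and Φ(-0.35) = 0.36.

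The loss is set by a - b, and the documents give no value for it. The first row also shows that a rule matching the suspension exactly would have little power at this size.

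**The case against.** **The cure rule carries no stated comparison.** It is one sentence under data collection. Cure is absent from the hypotheses and the outcome list, and section 2.10 assigns it no test. This is correct and limits the weight of the point. It does not remove it: the per-compartment rate that is listed has no threshold, and the rule that has a threshold covers one compartment.

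**Point C is measured and modelled.** It is measured at every visit and enters the mixed model, so it would be wrong to infer that the plan ignores the apex. The model as written still gives no C-specific group effect and no rate.

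**Ba is a reasonable criterion here.** Section 2.4 describes women with anterior wall prolapse, section 2.7 lists Aa or Ba > 0, and Ba may move with apical support. This stands, and Ba should be kept. The documents do not, however, justify it as a stand-in for C.

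**A reader might infer that the Ba cure rate mainly reflects anterior colporrhaphy.** The documents do not support that. They give neither the frequency of the repair nor its share in Ba, and randomisation balances co-procedures in expectation.

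**A reader might also infer that the Ba rule would hide an apical effect entirely.** That holds only if Ba is unrelated to the suspension. An example that sets anterior failure equal in both arms assumes this result and does not show it.

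**A better rule would still have low power.** True, as the working shows. The case for it is a correct definition fixed in advance, with no promise of a significant result.

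**Conclusion.** The point holds as a defect in a secondary definition. The only cure rule omits the compartment that the randomised suture suspends, it can misclassify in both directions, and the planned model does not make up for it. This rests on the text alone.

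The size of any lost apical difference cannot be derived from the documents. The range of 20 down to 0 points rests on the assumed 90% v 70% and on assumed links between Ba and the apex. The primary outcome, the sample size and the main conclusion are unaffected.

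It does not follow that C must become the main anatomical outcome, or that the -1 cut-off for Ba should be carried over to C. Nothing in the plan settles either.

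Sections 2.5 and 2.9 still speak of anterior colporrhaphy as the procedure under comparison, so the Ba rule may be carried-over text. That is an inference, and the point does not depend on it.

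**What to change.** - **Section 2.8 Data collection:** keep Ba as the anterior criterion, add prespecified apical (C) and posterior (Bp) criteria, and define overall anatomical cure as meeting all of them. The investigators should set and justify the cut-offs before any unblinded data are seen.
- **Section 2.8 Primary and secondary outcome measures:** name the per-compartment rates and the overall rate at 12 months, so that a suboptimal result has a stated meaning.
- **Section 2.10:** compare these rates between arms with a test suited to small counts, such as Fisher's exact test. With 90% v 70% and 21 per group, the expected failures per arm under no difference are 21 × 0.20 = 4.2, too few to rely on a chi-squared approximation. Add group-by-POP-Q-point and group-by-time terms that allow a 12-month group effect at C, or fit a separate model for C.

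The cost is protocol wording, since POP-Q is already recorded at baseline and each follow-up. The overall cure rate cannot exceed the Ba-only rate and will probably be somewhat lower. Power for these secondary rates is low at about 21 per group, so they should be reported with confidence intervals.
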